6.2 Exclusion criteria

- clinically significant unrelated illness which in the judgement of the investigators could compromise the patient's ability to tolerate the IMP or be likely to interfere with the study procedures or results
- known hypersensitivity reactions to prior application of E. coli-derived material
- women with breast-feeding activity
- concomitant use of any other investigational agent (agent for which there is currently no approved indication from regulatory authorities)
- > clinical application of any other drug with known antitumor activity
- prophylactic anticoagulation within the last 3 days

NOTE: Since this is a phase I study for end-stage cancer patients, patients who would be excluded from the protocol strictly for laboratory abnormalities only can be included at the Investigator's discretion. This will be documented as an exception to the criteria and will be signed and filed in the CRF and the Trial Master File.

Patient's eligibility for entry to the study will be assessed by the Investigator or their delegated representative physician. Distribution of **gender** in the study population will be random and gender will be no factor influencing accrual. tTF-NGR is not expected to differ in its effects in male and female patients.

Patients identified as eligible for entry into the study will be **registered** centrally through the study bureau of the Department of Medicine A (Hematology, Hemostaseology and Oncology) of the UKM.

tTF-NGR Phase I Study, Study Protocol, Version 10, 28.07.2016

7. Treatment Plan

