6.1 Inclusion Criteria

Inclusion criteria for entry on trial are

- \triangleright age \geq 18 years
- histologically proven or cytologically confirmed solid malignant tumor or malignant lymphoma
- recurrent or refractory disease after standard therapy and with no known curative or survival-prolonging treatment options according to the judgement of the investigators
- > life expectancy of at least 6 weeks according to the judgement of the investigators
- Karnofsky performance status ≥ 50
- measurable disease with at least one marker-lesion measurable in 2 dimensions by Vascular Volume-Fraction-MRI
- adequate bone marrow function with absolute neutrophil count 1000/microliter and platelet count > 50/nl.
- normal global coagulation parameters (Quick, PTT, TZ, fibrinogen), no prophylactic anticoagulation
- ➤ adequate liver function (total bilirubin < 3x the upper normal limit (ULN), SGPT/SGOT < 3x ULN)

- adequate renal function (serum creatinine < 3x ULN)

- > no history of coronary heart disease, stroke, transitory ischemic attacks, pulmonary embolism, or deep vein thrombosis
- \succ time elapsed from previous therapy (including other IMPs) \geq 3 weeks with recovery from side effects

>

- exclusion of central nervous system (CNS) disease and CNS vascular abnormalities by MRI
- ability to understand and provide written informed consent
- written informed consent given
- ➤ for female patients with child-bearing potential exclusion of pregnancy by adequate testing within 48 hours prior to entry on study
- females of childbearing potential as well as fertile males must agree to use a highly effective form of contraception (Pearl Index < 1) during the study and for 120 days following the last dose of the IMP

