7.1 Administration of tTF-NGR

Patients will receive their assigned dose of tTF-NGR as an i.v. infusion via central venous access (PORT-systems allowed) with an infusion duration of 1 hour at a constant rate. The IMP is stored at -80°C and will be thawed, solved in saline and filtered (Millipore filter unit, 0.2 μ m) short before application (see Appendix: Phase I: Rekonstitution tTF-NGR).

Potential side effects and toxicities anticipated can be classified as those related to infusional reactions, venous thrombosis, arterial vascular occlusion and embolism, disseminated intravascular coagulation (DIC), tumor bleeding, antibody formation, liver toxicity, and transient thrombocytopenia (see IMPD). Thus, treatment has to be performed obligatory in-house for the complete application time of 5 days with all appropriate drugs for hypertensive reactions, for fibrinolysis and anticoagulation ready to use and with appropriate transfusions of platelets and red blood cells available and prepared for. Constant back-up and information of the Intensive Care Unit (ICU) of the UKM is mandatory.

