Delays in dosing of the next application for up to 6 days in individual patients are allowed in case anticipated adverse events connected with the composition of the drug or the mechanism of action of tTF-NGR occur, which need to be addressed before treatment can continue. This is in particular foreseen in the following situations:

- 1. Consumption of platelets due to tumor vascular coagulation with platelet count drops to grade 3 of CTCAE version 4.0 (page 112; 25.000 50.000 platelets per microliter) to allow recovery of counts to >50.000 per microliter,
- 2. Infusional reactions due to the protein application in case tTF-NGR was applied without premedication (see below) to allow resolution to CTCAE grade <2 and a following application with premedication.

However, in patients with objective response and good toleration of the drug, who are further treated in the compassionate-use program with the IMP after completion of the Study Period, dosing delays and/or modifications are allowed and handled according to the judgement of the Investigators.

9. Dose Limiting Toxicity (DLT) and Maximum Tolerated Dose (MTD)

Dose Limiting Toxicity (DLT): DLT is defined as occurrence of toxicity of Grade 3 or more according to the revised NCI Common Terminology Criteria for Adverse Events (CTCAE) version 4.0 (http://ctep.cancer.gov) for non-hematological toxicity or Grade 4 or more for hematological toxicity. DLT must be considered by the investigator as being causally related to the IMP. In case the investigator comes to no decision, the data safety monitoring board is to be involved. Intensity of toxicity will be graded according to CTCAE using a five-point scale:

α	
C	L

Grade	Equivalent To:	Definition
Grade 1	Mild	Mild; asymptomatic or mild symptoms; clinical or diagnostic observations only; intervention not indicated.
Grade 2	Moderate	Moderate; minimal, local or noninvasive intervention indicated; limiting age-appropriate instrumental Activities of Daily Living (ADL).
Grade 3	Severe	Severe or medically significant but not immediately life-threatening; hospitalization or prolongation of hospitalization indicated; disabling; limiting self care ADL.
Grade 4	Lifethreatening/Disabling	Life-threatening consequences; urgent intervention indicated
Grade 5	Death	Death related to AE.

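### The laboratory waiver in Section 6.2 sets no lower limit for platelets or coagulation and needs no second approval, although the drug is procoagulant

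*Combined protocol and SAP*

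**What the plan says.** Section 6.1 sets the laboratory limits. For blood counts it requires "adequate bone marrow function with absolute neutrophil count 1000/microliter and platelet count > 50/nl", and for clotting "normal global coagulation parameters (Quick, PTT, TZ, fibrinogen), no prophylactic anticoagulation".

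The NOTE at the end of Section 6.2 then lets patients who would be "excluded from the protocol strictly for laboratory abnormalities only can be included at the" Investigator's discretion. The reason given is that this is a phase I study in end-stage cancer patients. The condition attached is that the exception is documented, signed and filed in the CRF and the Trial Master File.

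Section 3.6 describes tTF-NGR as keeping its full procoagulatory activity. Section 7.1 anticipates infusional reactions, venous thrombosis, arterial occlusion and embolism, and also "disseminated intravascular coagulation (DIC), tumor bleeding, antibody formation, liver toxicity, and transient thrombocytopenia (see IMPD"). Section 14.9 reports transient platelet drops already seen in single patients, possibly from consumption within the tumor vessels.

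Section 8 gives the Grade 3 platelet range and the level to which counts should recover when a dose is delayed: "25.000 50.000 platelets per microliter) to allow recovery of counts to >50.000 per microliter". Section 9 defines hematological DLT as "Grade 4 or more for hematological toxicity. DLT must be considered by the investigator as being causally related to the IMP".

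**The concern.** A waiver of laboratory limits is a common phase I choice. Here, however, platelets and clotting tests are the laboratory criteria closest to the drug's expected harms, and the NOTE treats them like any other value. As written, one physician's signature is enough to give a procoagulant drug to a patient with a very low platelet count or with clotting results that suggest consumption.

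For platelets there is a second consequence. The hematological DLT is defined by the grade reached, not by the change from entry. A drug-related fall that would not be a DLT from a baseline meeting Section 6.1 can be one from a waived baseline. Such an event can enter the MTD process at three points:

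- as the escalation patient's first DLT, which opens the verification group and counts as one of its six patients (Sections 9 and 10);
- as the further DLT that closes the verification group and forces de-escalation (Sections 9 and 10);
- as one of the two in six that drive de-escalation further at a lower level (Section 10).

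**Working it through.** **Does anything else restore an entry limit?** The plan states no figure on this point, so the first check is textual.

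- *Scope of the NOTE.* It sits under the exclusion criteria, but it speaks of patients excluded from the protocol. That includes patients who miss a laboratory limit in Section 6.1. No parameter is named as exempt.
- *Other exclusions in Section 6.2.* The criterion "clinically significant unrelated illness which in the judgement of the investigators could compromise" tolerance of the drug is also a matter of investigator judgement. It concerns unrelated illness, so a low count caused by the cancer itself arguably falls outside it.
- *Section 8.* It permits a delay of up to 6 days after an on-treatment platelet drop. It is not an entry rule.
- *Section 9.* "In case the investigator comes to no decision, the data safety monitoring board is to be involved" applies to undecided DLT causality, not to eligibility.
- *Section 13.1.* An unchanged or improved baseline finding is not an adverse event. This does not cover a further fall.
- *Section 7.1.* In-house treatment, prepared transfusions and ICU back-up respond to harm. They do not limit who is exposed.

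None of these sets a lower limit.

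**How far must platelets fall to reach the DLT boundary?**

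Inputs:

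- Entry limit: 50/nl (Section 6.1), which is 50,000 per microliter.
- Grade 3 range: 25,000 to 50,000 per microliter (Section 8).
- Grade 4: the protocol does not print a value. I take it as below the lower end of the Grade 3 range, that is, below 25/nl.

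Formula: relative fall needed from baseline b = (b − 25) / b.

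| Baseline (per nl) | Fall needed (per nl) | Relative fall |
|---|---|---|
| 150 | 125 | 125/150 = 83.3% |
| 100 | 75 | 75/100 = 75.0% |
| 51 | 26 | 26/51 = 51.0% |
| 50 | 25 | 25/50 = 50.0% |
| 49 | 24 | 24/49 = 49.0% |
| 40 | 15 | 15/40 = 37.5% |
| 30 | 5 | 5/30 = 16.7% |
| below 25 | none | already in the Grade 4 range |

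This is a gradient, not a step at 50/nl. Going from 51/nl to 49/nl changes the required fall by only two percentage points. The difficulty is that the waiver has no lower end. In the last row the absolute grade is already met before dosing, so whether a DLT is counted would rest wholly on the causality judgement.

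**Can this be turned into an effect on the MTD?** No. That would need the frequency of waivers, the distribution of waived baselines, the depth of drug-related platelet drops and the underlying DLT rate. The documents give none of these; Section 14.9 reports earlier drops without their size. I have therefore calculated no probability.

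**The case against.** The strongest reply is that discretion is defensible here. The patients have no remaining standard options, the trial runs in one hematology and hemostaseology department, each exception is signed and filed, and treatment is in-house with ICU back-up. The waiver applies only where laboratory values are the sole obstacle. A history of coronary disease, stroke, TIA, pulmonary embolism or deep vein thrombosis, and prophylactic anticoagulation, stay non-waivable. Section 12 has eligibility checked weekly as well as before treatment, Section 7.4 stops treatment in patients who become unfit, and the DSMB reviews safety data (Section 12.4.1). All of this stands and lowers the risk. None of it sets a limit at entry.

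Four stronger readings are tempting, and the documents do not support them.

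- *A reader might infer that an abnormal clotting baseline makes DIC undetectable or produces false DLTs.* It does not. The baseline is recorded, and coagulation is tested before dosing, at infusion stop, at 1 and 5 hours, daily, on day 5 and weekly (Section 12). Section 12.1 also measures markers that are not entry criteria: D-dimers, fibrin split products, alpha 2 AP and AT III.
- *A reader might infer that Section 8 contradicts the NOTE.* It does not, because the delay is permitted, not required, and concerns on-treatment drops. It shows only that 50,000 per microliter is the protocol's own recovery level.
- *A reader might infer that the MTD will be biased.* A single such event does not set the MTD: a first DLT leads to up to five more patients, and a second is needed. Every DLT must also be attributed to the drug, and a low count at entry offers another explanation. The possibility is real, but its size is unknown.
- *A reader might infer that every clotting deviation should bar entry.* Section 6.1 asks for normal values. Without any waiver, a trivially prolonged PTT or a slightly raised fibrinogen would exclude a patient for little safety gain.

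**Conclusion.** The point holds as a patient-safety gap. The NOTE permits unlimited departure from the platelet and coagulation limits on one physician's decision, for a drug whose anticipated toxicities include DIC, tumor bleeding and thrombocytopenia.

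For platelets only, the gap also reaches the primary endpoint, through a DLT definition that ignores baseline. The size that can be stated is the required fall: 50% from 50/nl against 17% from 30/nl, and none below 25/nl. This rests on reading Grade 4 as below the Grade 3 range printed in Section 8, and it matters only if deep waivers are actually granted. A waiver just under 50/nl changes little. No effect on the MTD is claimed, because the documents do not allow one to be estimated. This is an inexpensive improvement to make, not a flaw that invalidates the design.

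**What to change.** Add to the NOTE in Section 6.2:

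*This exception does not apply to the platelet count (>50/nl). Deviations in Quick, PTT, TZ or fibrinogen may be waived only if minor, not suggestive of consumptive coagulopathy or bleeding tendency, and agreed with the sponsor or DSMB before dosing.*

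The platelet clause uses the protocol's own limit, which is also the Section 8 recovery level. The coagulation clause keeps room for trivial deviations but adds a second opinion where the hazard lies. The waiver for liver, renal and neutrophil values stays as it is, and no extra DLT reporting is needed for patients waived on those.

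The cost is two sentences in the protocol. A few end-stage patients with platelets at or below 50/nl would be turned away, including some only marginally outside the limit, and each coagulation waiver would need a short agreement before dosing.

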7.1 Administration of tTF-NGR

Patients will receive their assigned dose of tTF-NGR as an i.v. infusion via central venous access (PORT-systems allowed) with an infusion duration of 1 hour at a constant rate. The IMP is stored at -80°C and will be thawed, solved in saline and filtered (Millipore filter unit, 0.2 μ m) short before application (see Appendix: Phase I: Rekonstitution tTF-NGR).

Potential side effects and toxicities anticipated can be classified as those related to infusional reactions, venous thrombosis, arterial vascular occlusion and embolism, disseminated intravascular coagulation (DIC), tumor bleeding, antibody formation, liver toxicity, and transient thrombocytopenia (see IMPD). Thus, treatment has to be performed obligatory in-house for the complete application time of 5 days with all appropriate drugs for hypertensive reactions, for fibrinolysis and anticoagulation ready to use and with appropriate transfusions of platelets and red blood cells available and prepared for. Constant back-up and information of the Intensive Care Unit (ICU) of the UKM is mandatory.

7.2 General concomitant medication and supportive care

Concomitant therapy and supportive care will be provided as deemed necessary by the Investigators and according to the institutional guidelines.

7.3. Other anti-cancer medication

Administration of any other anti-cancer medication including chemotherapy and biologic therapy and other IMPs is not permitted during study period. Palliative radiotherapy of single tumor-lesions e.g. causing tumor-related pain is allowed, however, these lesions have to be excluded from response judgement.

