Patients will be treated with tTF-NGR by 1-hour iv infusions via central venous access daily for 5 days every 3 weeks. Starting dose will be 1 mg/m²/day. Intraindividual dose escalation will be performed within one single patient in 0.5 mg/m²/day steps upon good toleration of the previous cycle. Patients within the dose-escalation part will be treated in sequence and not in parallel. Individual patients can undergo a maximum of 8 dose-escalations. The maximum number of 8 dose escalations is reached only if stable disease (SD) is ongoing upon 8 cycles of therapy. Dose-escalation is stopped before the maximum number of 8 escalation steps if tumor response, tumor progression or a Dose-Limiting Toxicity (DLT) is observed. In the case of SD and with good tolerability these patients can obtain further cycles without dose-escalation until tumor progression or Dose-Limiting Toxicity (DLT) and the next patient can start with dose-escalation cycles on the highest tolerable dose for the previous patient. A patient will undergo no further treatment if any of the criteria under 7.4 is reached.

Treatment will be followed by MRI tumor perfusion studies at cycles as decided by the Investigator as a surrogate marker for target-hit. MRI tumor perfusion studies will be performed before treatment onset, on day 1 (4-6 hours after application), and on day 5. MRI will be done not in every cycle of every patient, but in every patient of the verification cohorts in at least one cycle.

Toxicity monitoring will be performed according to the most recent version of the CTC criteria.

MTD is the dose below the dose leading to reproducible episodes of Dose Limiting Toxicity (DLT). DLT will be characterized by clinical, blood and serum monitoring at specified time points before and during study period.

Antitumor activity and response will be determined according to RECIST criteria with extent of disease evaluation before and after treatment period and in 3-monthly intervals thereafter, or as defined by clinical needs. Waterfall-analysis for response quantification in % of the marker lesions before treatment onset and at best response will be done centrally by the study radiologist.

Pharmacokinetic monitoring will be done as outlined below.

6. Eligibility criteria and patient registration

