Starting dose will be 1 mg/m²/day. Intraindividual dose-escalation will be performed in 1 patient in 0.5 mg/m²/day steps (to a maximum of 8 cycles) upon a rest period of 16 days for the next treatment cycle of 5 days. The maximum number of 8 dose escalations is reached only if stable disease (SD) is ongoing upon 8 cycles of therapy. Dose-escalation is stopped before the maximum number of 8 escalation steps if tumor response, tumor progression or a Dose-Limiting Toxicity (DLT) is observed. If tumor response is observed or if a patient is diagnosed with progressive disease (PD) after ≥ 2 cycles or clinically as judged by the investigator even before 2 cycles, this patient will go off study and will be replaced by a further patient in whom individual dose escalation will be resumed, starting with the highest dose level reached without DLT in the previous patient. When any DLT is observed in this patient, intraindividual dose escalation is stopped and the patient is taken off study. In case of stable disease or response and resolution of the DLT this patient can be further treated on the highest tolerable dose level without DLT until any of the criteria under 7.4 is reached. This treatment will then be given on an individual compassionate-use basis (off study) according to § 34 of the Helsinki declaration (2013, Fortaleza; Post-Trial Provision).

If this first observed DLT is nonfatal, up to 5 more patients will then be treated on the same dose level having caused DLT (verification group). Patients of the verification group will be treated in sequence of each other, thus a patient has to tolerate the first cycle (5 days) and the rest period of 16 days without DLT before the next patient can be added to this verification group.

Upon observation of no additional DLT in the verification group in a minimum of 2 cycles for each patient, dose escalation can be resumed in one patient out of these until DLT (continue as above). The remaining patients in the verification group will be further treated at this dose-level until any of the criteria under 7.4 is reached.

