Start 1 pt at 1 mg/m²/day with individual dose escalation at 0.5 mg/m²/day for 5 days every 3 weeks until any DLT (= dose "d1") or to a max of 8 cycles

Verification group (VG) of ≤5 further pts at d1 without indiv. dose esc.

(Verification group (VG) of ≤5 further pts at d1-0.5mg/m²/day without indiv. dose esc. in case a death occurs as DLT)

No further DLT in VG > resume dose escalation: start 1 pt of VG at d1 + 0.5 mg/m²/day (d), then as above

1 further DLT in VG > dose de-escalation d1 - 0.5 mg/m²/d, 5 further pts (d-1(-2))

>1 further DLT: d-1 = MTD

>1 further DLT > dose de-escalation, continue as above
```

Again, if a patient has been taken off the study due to a DLT or progressive disease, the patient may further be treated as follows. If the patient has stable disease or response and the DLT has been resolved, outside the study the patient may be treated

with the study medication on the highest tolerable dose level without DLT (§ 34 Declaration of Helsinki, Fortaleza 2013). In case of progressive disease or if the DLT has not been resolved, different treatment options are offered.

11. Study objectives and end-points

Primary Objectives

To evaluate the maximum tolerated dose (MTD) and the dose-limiting toxicity (DLT) of intravenously (i.v.) infused daily applications of tTF-NGR in patients with cancer (solid tumors and lymphomas), who had obtained all standard treatment known for their disease entity prior to entry on study.

Secondary Objectives

- 1. To determine the perfusion and vascular volume fraction of measurable tumor lesions versus normal reference tissue before and after tTF-NGR application by MRI as a imaging surrogate parameter for biological activity of the IMP.
- 2. To obtain pharmacokinetic data of tTF-NGR.

Primary Safety end-point

Maximum Tolerated Dose (MTD). MTD is the dose below the dose leading to reproducible episodes of Dose Limiting Toxicity (DLT) in at least 2/6 patients. DLT will be characterized by clinical, blood and serum monitoring at specified time points before and during study period.

Secondary Safety end-points

- 1. Occurrence and frequency of inhibition of tumor blood flow as measured by contrast-enhanced Magnetic Resonance Imaging (MRI).
- 2. Occurrence and frequency of tumor response defined as Complete Response (CR), Partial Response (PR), or Stabile Disease (SD) as defined by RECIST criteria.

Descriptive statistics will be used.

12. Patient evaluation and follow-up

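### Section 7.3 removes irradiated lesions from the response assessment without preserving growth seen before irradiation, so the CR/PR/SD frequency and the waterfall could lean toward benefit

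*Combined protocol and SAP*

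**What the plan says.** Section 7.3 states: "Palliative radiotherapy of single tumor-lesions e.g. causing tumor-related pain is allowed". Pain is given as an example, so other reasons for irradiating a lesion are not ruled out. The only consequence for the assessment is that "these lesions have to be excluded from response judgement". No condition is attached.

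The other relevant places are these:

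- **Entry (Section 6.1).** The requirement is "measurable disease with at least one marker-lesion measurable in 2 dimensions by Vascular Volume-Fraction-MRI", so one marker lesion is enough.
- **Endpoint (Synopsis and Section 11).** The secondary endpoint is the occurrence and frequency of "tumor response defined as Complete Response (CR), Partial Response (PR), or Stabile Disease (SD) as defined by RECIST criteria". Stable disease therefore counts as a response. On the analysis, the plan says "Descriptive statistics will be used".
- **Continuous measure (Section 5).** The plan is a "Waterfall-analysis for response quantification in % of the marker lesions before treatment onset and at best response", read centrally by the study radiologist. Irradiated lesions are not mentioned.
- **Progression (Sections 7.4, 10 and 16.1).** Progression ends study treatment, and the investigator may diagnose it clinically. Neither provision is linked to radiotherapy.
- **Disease assessment (Section 15).** It refers to RECIST in general and has no rule for irradiated lesions.

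**The concern.** Whether a lesion comes to palliative radiotherapy during treatment plausibly depends on how it is behaving. If painful or growing lesions are the ones irradiated, removing them makes the set of assessed lesions depend on the outcome, and the better-behaved lesions determine the RECIST category and the waterfall value.

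This endpoint is more exposed than most. Because SD counts as a response, a patient who moves from PD to SD moves from failure to success. With one marker lesion sufficient for entry, a single irradiation can also leave nothing to assess, and the protocol does not say how that patient is classified or whether the patient stays in the denominator.

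The same classification is used in running the trial. Section 10 replaces an escalating patient who has PD, and says: "The maximum number of 8 dose escalations is reached only if stable disease (SD) is ongoing upon 8 cycles of therapy".

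**Working it through.** **1. The plan's own figure.** Section 16.1 gives a minimum of 7 patients. It is a count driven by DLT: 1 escalation patient with DLT + 1 verification patient with DLT + 5 patients one step lower = 7. This reproduces the stated figure. Response plays no part in it.

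**2. Effect on one patient.** The documents give neither lesion sizes nor a numerical progression threshold. Both are assumed here: diameters of 40 and 30 mm, and PD at an increase of 20% in the sum. The first lesion grows to 56 mm and is irradiated; the second is unchanged.

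- Lesion kept: (56 + 30)/(40 + 30) − 1 = 86/70 − 1 = +22.9%, which is PD at the assumed threshold.
- Lesion removed from both sums: 30/30 − 1 = 0%, which is SD.

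In this example the category changes once the sum has risen by 0.20 × 70 = 14 mm, that is, once the first lesion reaches 54 mm.

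**3. Range over the assumptions.** Take k equal lesions, one of which grows by a fraction g and is irradiated. The change in the sum is g/k with the lesion kept and 0 with it removed.

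| Lesions (k) | g = 20% | g = 50% | g = 100% | Lesion removed |
|---|---|---|---|---|
| 1 | +20.0% | +50.0% | +100.0% | nothing left to assess |
| 2 | +10.0% | +25.0% | +50.0% | 0% |
| 3 | +6.7% | +16.7% | +33.3% | 0% |
| 5 | +4.0% | +10.0% | +20.0% | 0% |

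Removal erases all the recorded growth at any threshold. Whether the category changes depends on the number of lesions and the growth: at 20% it does so in 4 of the 9 combinations with two or more lesions, one of them exactly at the threshold.

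**4. Effect on the reported frequency.** One reclassified patient moves it by 1/N:

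- N = 7: 14.3 percentage points
- N = 12: 8.3 points
- N = 18: 5.6 points

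At N = 7, for example, 1/7 = 14.3% (exact 95% CI 0.4 to 57.9%) becomes 0/7 = 0% (0 to 41.0%).

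**5. What cannot be calculated.** The documents do not say how often radiotherapy is expected on study, or how often it would be given to a growing lesion. The expected bias therefore cannot be estimated.

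**The case against.** The strongest reply is that the exclusion itself guards against bias: without it, shrinkage caused by radiotherapy would be credited to tTF-NGR. That stands, and the exclusion should be kept for measurements taken after irradiation. A painful lesion that is stable or shrinking would also be removed, which can lower the apparent benefit, so the direction of bias is plausible but not certain.

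A second reply is that growth would often be caught anyway. The Section 12 calendar, headed as applying to each cycle, lists tumour measurements in the week before treatment, and PD may be called clinically. This is partial protection. Section 5 words the assessment schedule differently, the clinical call is discretionary, and neither is triggered by irradiation.

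A third reply is that the endpoint is secondary and descriptive, and that a one-patient shift lies well inside the interval in step 4. This is true and limits the weight of the point. Imprecision does not excuse an avoidable systematic error, however, and the frequency and the waterfall are the trial's main summaries of antitumour activity.

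A reader might infer more than the documents support:

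- **That 7.3 reverses a progression already recorded.** It does not say so, and 7.4 makes no exception for irradiated lesions. The gap is that growth before irradiation is not expressly preserved.
- **That dropping the lesion only at follow-up creates a false PR** (30/70 − 1 = −57%). The ordinary meaning of excluding a lesion is to exclude it throughout, so this reading is implausible.
- **That a patient with no marker lesion left drops out of the denominator.** The protocol does not define the denominator either way.

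**Conclusion.** The point holds as a gap in endpoint scoring. Followed as written, 7.3 can remove lesions in a way that depends on outcome, and no other section says that growth before irradiation counts or how a patient with no remaining marker lesion is classified. The CR/PR/SD frequency and the waterfall could be biased toward benefit; the documents do not show that they will be.

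The size is 14.3 percentage points per reclassified patient at the minimum of 7. The number of such patients is unknown. The lesion sizes and the 20% threshold are assumptions that illustrate the mechanism; they do not estimate its frequency.

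It might also be inferred that the MTD is affected, because SD versus PD decides whether an escalating patient continues. The documents do not support this. The MTD rule counts DLTs, and a replacement patient resumes at the highest level reached without DLT, so the classification mainly changes who is escalated. The minimum of 7 is likewise unaffected.

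**What to change.** Add a scoring rule to Section 7.3 and Section 15, limited to how the endpoint is classified:

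1. Count the last measurement before irradiation, together with all other lesions, in the RECIST category up to that date. Growth that meets PD is scored as PD.
2. For later percentages and the waterfall, remove the irradiated lesion from both the baseline sum and the follow-up sum.
3. Keep a patient with no remaining marker lesion in the denominator. Retain the best category documented before irradiation (CR, PR or SD); if none was documented, count the patient as not responding. Naming SD here matters because the endpoint treats SD as a response.

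The cost is a few sentences and a reading instruction for the study radiologist. No extra patients are needed, and the rule uses measurements already taken. The downside is a possibly somewhat lower reported CR/PR/SD frequency. One limit remains: growth between the last measurement and irradiation is still not captured.
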